Title

Applying Long-term Follow-up to Improve Patient Selection in Laparoscopic Anti-reflux Surgery

Aim

The aim of this study is to use patient-reported and register-based long-term follow-up after anti-reflux surgery, to investigate treatment effect and use the results to establish a clinically applicable scoring system to ensure optimal selection of patients for surgical treatment of gastroesophageal reflux disease.

Background

Episodic reflux of gastric contents to the esophagus is physiological but is considered gastroesophageal reflux disease (GERD) when accompanied by bothersome symptoms, typically heartburn, regurgitation or retrosternal pain. Extra-esophageal symptoms such as asthma, laryngitis and chronic cough may also occur (1). GERD is a complex and multifaceted disease (2,3), affecting 10-20% of the Western population (4) and has been shown to significantly reduce the quality of life (5). Worldwide, the prevalence of GERD has been increasing (6-8).

Treatment of GERD consists of anti-secretory drugs, mainly proton pump inhibitors, or anti-reflux surgery. Laparoscopic anti-reflux surgery is considered standard of care in surgical treatment of gastro-esophageal reflux disease (9) and with careful patient selection based on thorough preoperative workup (10); symptom control and patient satisfaction are high compared to medical therapy (11,12).

Despite a tailored approach, laparoscopic anti-reflux surgery is not without risks of adverse effects, most notably disruption of the fundoplication, post-fundoplication dysphagia and gas-bloat-syndrome, in some cases leading to reoperation (13-18). Furthermore non-surgical factors such as pre-existing anxiety or depression disorders can influence postoperative satisfaction and symptom relief when compared to patients without concomitant psychological disorders (19).

Although few studies conclude that medical and surgical treatment of GERD have similar effectiveness, disease-specific quality of life generally improves after anti-reflux surgery and patient satisfaction is high. Depending on surgical procedure, the postoperative quality of life, ranges from significantly increased compared to preoperative measurements, to “normal” values as found in subjects devoid of GERD (20-33). 73-98% are satisfied with their condition after surgery and would choose surgery again (22,32-38).

Laparoscopic anti-reflux surgery is more effective than medical management with regard to short to medium length follow-up (12,34,35). Few studies provide long-term follow-up. After ten years, the benefits of surgery seem to decrease, but there is still a significant improvement in quality of life compared to preoperative measurements (36,39). Known causes of dissatisfaction are postoperative complication, redo-fundoplication and developing new bothersome symptoms such as gas-bloat and dysphagia combined with inadequate symptom relief (37,40).

Follow-up of randomized clinical trials have demonstrated, that anti-reflux surgery patients use acid suppressing drugs, primarily proton pump inhibitor (PPI) therapy at postoperative follow-up. Use have been considered minimal with <20% using PPI-therapy (35) and 27-44% using PPI at five-year follow-up (38). A recent register-based study (41), demonstrated a greater number of redeemed prescriptions of proton

pump inhibitor after primary anti-reflux surgery, than previously known. Five-, 10- and 15-year risks of long-term PPI use were 29.4%, 41.1% and 56.6%. However, this register-based study could not examine whether patients had objective recurrence of reflux disease and also did not examine indication for treatment as well as prescribing physician. From 2001 to 2011, 94.4% of PPI where prescribed in primary care (42) and it is unknown why post-fundoplication patients are prescribed PPI. It has previously been demonstrated, that the use of acid suppressing drugs after anti-reflux surgery does not necessarily correlate with abnormal acid exposure to the esophagus (43,44). In general, the use of PPI has increased rapidly in Denmark, rising 243% from 2001 to 2011 despite more restrictive guidelines and changes in reimbursement (42). As the majority of proton pump inhibitors are prescribed by general practitioners and not by the surgical centers, surgeons have very little knowledge of this aspect of life following anti-reflux surgery.

This study is part of the PhD project entitled: "Utilization, outcome and development of laparoscopic anti-reflux surgery" originating from the University of Southern Denmark (Protokol #: SDUSF-2016-115-(682)).

Methods and analysis

The study is a retrospective cohort study utilizing data from patient records and follow-up with patient-reported quality of life as well as registry-based data.

Study population

The study population consists of all adult patients (age ≥ 18) having undergone laparoscopic anti-reflux surgery (Nomesco Classification of Surgical Procedures (NCSP) (45): KJBC01) from January 1, 2002 to December 31, 2013 in The Department of Surgery, Kolding Hospital, a part of Lillebaelt Hospital Denmark (n=557). Patients will be identified through Lillebaelt Hospital's Patient Administrative System. Day of surgery will be considered index date.

Date of follow-up will be the date, patient filled out quality of life questionnaires as described below. For patients deceased since index date, permission to include data from electronic patient records and registry-based data will be applied for from The Danish Patient Safety Authority.

All patients will be contacted by the existing Danish national digital communication system (e-Boks) and asked to participate in the study. Patients exempt from using the system, will be contacted by letter. Only patients providing informed consent will be included in the study.

Data sources

Data for the study will consist of electronic patient records, follow-up with patient-reported quality of life measurements and registry-based data.

Electronic patient records

From the electronic patient records, the following data will be identified: age (years), sex (male/female), body mass index (kg/m^2), alcohol consumption (drinks of 12g ethanol per week), tobacco use (current, former or never-smoker), ASA-score, Charlson Comorbidity Index (CCI) (46) and previous abdominal surgery (yes/no).

Preoperative endoscopically verified occurrence of hiatal hernia (yes/no), esophagitis (yes/no) will be included as well as, from 24-hour pH-measurement and esophageal manometry, reflux-index (%), symptom correlation (%) and presence of esophageal motility disorder (hypomotility, normal motility or hypermotility). Patients preoperative reflux symptoms defined as typical symptoms (yes/no), atypical symptoms (yes/no) and dysphagia (yes/no) are included as are surgical data included duration of surgery (minutes), type of fundoplication (270° Toupet/360° Nissen), Length of hospital stay (days), per- and postoperative complications registered within 30 days as defined by Clavien-Dindo (47).

Quality of life follow-up

Patients will be contacted as described above and asked to answer validated questionnaires regarding disease-specific quality of life (GERD-HRQL) (48) and dysphagia (Dysphagia Handicap Index) (49). Patients will also be asked if they are currently taking PPI (yes/no), in what dosage (never/when needed/once daily/twice daily), which symptoms have warranted PPI-use (reflux symptoms/dysphagia/gastritis/preemptive against peptic ulcer disease/other) and which physician prescribed the drug (general practitioner/surgeon/other doctor at hospital/other specialist in private practice)

Registries

All Danish inhabitant are issued with a civil registry number at birth or at date of moving to Denmark. The civil registry number are a unique personal identifier and is used across a variety of nationwide databases with regards to health, financial and educational data. Data from the following nationwide Danish registries will be included in the study:

The National Patient Registry (NPR) on re-operative surgery (NCSP: KJBC00-02, KJBW96-98, KJBB00-01, KJBB96-97) and endoscopy (NCSP: KUJD02-05, KJCA55) during follow-up). NPR contains records of all discharge diagnosis since 1977 and all outpatient diagnosis since 1994 (50,51). All performed procedures, including endoscopies and surgeries are also registered using NCSP.

The National Patient Registry of Psychiatry (NPR-PSYK) on psychiatric diagnoses (ICD-10: F01-F99) in a two-year period before primary surgery. NPR-PSYK is a sub-registry of NPR and specifically contains records of all psychiatric discharge and outpatient diagnosis from psychiatric departments since 1995 (50,51).

The Civil Registry on marital status, 90-day mortality after primary surgery and all-cause mortality during follow-up. The Danish Civil Registry maintains complete records of births, deaths, civic status and emigration status of the entire Danish population based on civil registration number (52).

The Danish National Prescription Registry on use of anti-reflux medication (ATC: A02BA, A02BC, A02BX), anti-thrombotic treatment (ATC: B01A), non-steroid anti-inflammatory drugs (NSAID) (ATC: M01A) and selective serotonin reuptake inhibitors (SSRI) (ATC: N06AB) in a time period beginning two years before surgery and ending at end of follow-up. The Danish National Prescription Registry contains information on all sale of prescription drugs including date of sale, Anatomical Therapeutic Chemical Classification (ATC) code, civil registration number of buyer and package volume since 1994 (53).

Statistics Denmark on educational level at time of primary surgery (54) defined by ISCED (55), occupation status (employed/unemployed/retired) (56) and equivalent annual income in the year preceding primary surgery (57).

Primary outcome

Primary outcome of the study is treatment success or failure, with failure defined for each patient as at least one of the following statements being fulfilled:

1. Having undergone reoperation (NSCP: KJBC00-02, KJBW96-98, KJBB00-01, KJBB96-97) between index date and end of follow-up.
2. Having filled prescription of >60 DDD/year of PPI in any year between index date and end of follow-up.
3. Having no measure ≥ 3 on GERD-HRQL indicating symptoms being bothersome every day.
4. Having no measure ≥ 4 on Dysphagia Handicap index indicating symptoms being a moderate problem.

Date of failure will be defined as follows: In case of 1), date of failure will be date of reoperation. In case of 2), date of failure will be date of first prescription filled in the year, where >60 DDD of PPI are filled. In case of 3) or 4), date of failure will be end of follow-up.

Secondary outcomes

Secondary outcome will be 90-day mortality after primary surgery, rate of reoperation, use of PPI in DDD/year, use of PPI at follow-up (including indication and prescribing physician) and Quality of life defined by GERD_HRQL, Dysphagia Handicap Index.

Statistical analysis

Contingency tables

Contingency tables will be created listing:

- 1) Patient characteristics: Age (median), sex (male/female), body mass index (kg/m^2), alcohol consumption (drinks of 12g ethanol per week), tobacco use (current, former or never-smoker), ASA-score, CCI, preoperative psychiatric diagnoses, use of anti-reflux medication (yes/no), NSAID (yes/no) and SSRI before surgery (yes/no) and previous abdominal surgery (yes/no), educational level at time of primary surgery (ISCED), occupation status (employed/unemployed/retired) and equivalent annual income in the year preceding primary surgery.
- 2) GERD characteristics: Symptom profile: typical symptoms (yes/no), atypical symptoms (yes/no) and dysphagia (yes/no), endoscopically verified occurrence of hiatal hernia (yes/no), esophagitis (yes/no), measures from 24-hour pH-measurement and esophageal manometry: reflux-index (%), symptom correlation (%) and presence of esophageal motility disorder (hypomotility, normal motility or hypermotility).

- 3) Operative characteristics: Duration of surgery (minutes), type of fundoplication (270° Toupet/360° Nissen), length of hospital stay (days), per- and postoperative complications registered within 30 days as defined by Clavien-Dindo and 90-day mortality.
- 4) Follow-up: Rate of reoperation (%), use of PPI in DDD/year, use of PPI at follow-up (including indication and prescribing physician), GERD-HRQL and Dysphagia Handicap Index.

Categorical and continuous variables will be compared using Chi², Fisher's Exact Test and Kruskal-Wallis-test where appropriate.

Cox regression

Cox regression will be performed with treatment success as dependent variable, time to end of follow-up (as defined above) and the following variables will be tested and included as independent variables where appropriate: Age (median), sex (male/female), body mass index (kg/m²), alcohol consumption (drinks of 12g ethanol per week), tobacco use (current, former or never-smoker), ASA-score, CCI, preoperative psychiatric diagnoses, use of anti-reflux medication (yes/no), NSAID (yes/no) and SSRI before surgery (yes/no) and previous abdominal surgery (yes/no), educational level at time of primary surgery (ISCED), occupation status (employed/unemployed/retired) and equivalent annual income in the year preceding primary surgery, typical symptoms (yes/no), atypical symptoms (yes/no) and dysphagia (yes/no), endoscopically verified occurrence of hiatal hernia (yes/no), esophagitis (yes/no), measures from 24-hour pH-measurement and esophageal manometry: reflux-index (%), symptom correlation (%) and presence of esophageal motility disorder (hypomotility, normal motility or hypermotility), type of fundoplication (270° Toupet/360° Nissen).

Clinical scoring system

Using results from the Cox regression and using the methods for validation described by Steyerberg et al (58), a clinical scoring system will be developed with the purpose of identifying probability of treatment success based on preoperative known variables.

Dataflow

Data collected from electronic patient records and patient-reported quality of life follow-up will be stored using RedCAP (REDCap 7.4.23, Vanderbilt University, Nashville, TN, USA) hosted by OPEN - Odense Patient Data Explorative Network, Department of Clinical Research, University of Southern Denmark and Odense University Hospital, Denmark. Data will be transferred to Statistics Denmark and merged with registry-data. All analysis will be performed using STATA15 (StataCorp, College Station, TX, USA) on the servers of Statistics Denmark.

Ethics and dissemination

The study has been approved and registered at Lillebaelt Hospital according to current Danish Law and has previously been approved by The Danish Data Protection Agency (Permission #17/1942). Generated datasets will be stored on the servers of Statistics Denmark in compliance with Danish and EU-regulations

on personal health data and will be anonymized after merging, so that the unique personal identifier is removed.

Permission to contact patient for the project will be obtained from The Danish Patient Safety Agency. Each patient must consent to inclusion in the study, including the use of electronic patient records and registry-based data as described above. For deceased patients, permission for use of electronic patient records and registry-based data will be obtained from The Danish Patient Safety Agency. Specific permission for use of registry-based data will be obtained from The Danish Health Data Authority and Statistics Denmark.

The results of the study will be published in peer-reviewed medical journals regardless of whether these are positive, negative or inconclusive. Two peer-reviewed articles are expected to come from this study: one including the primary results, and one calculating a clinical scoring system based on the results.

References

1. Madanick RD. Extraesophageal presentations of GERD: where is the science? *Gastroenterol Clin North Am* [Internet]. 2014;43(1):105–20. Available from: http://www.ncbi.nlm.nih.gov/entrez/query.fcgi?cmd=Retrieve&db=PubMed&dopt=Citation&list_uids=24503362

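### The cohort is not restricted to first anti-reflux operations and no registry look-back is planned, so a redo can enter as the index operation

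*Combined protocol and SAP*

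**What the plan says.** Under Study population: "The study population consists of all adult patients (age ≥ 18) having undergone laparoscopic anti-reflux surgery", with the code and window given as "KJBC01) from January 1, 2002 to December 31, 2013 in The Department of Surgery, Kolding Hospital" and the size as "a part of Lillebaelt Hospital Denmark (n=557". Patients are found through the local hospital's administrative system. The index date is set in one sentence: "Day of surgery will be considered index date". No sentence requires a first operation, excludes earlier anti-reflux surgery, or says which operation is the index if a patient has two.

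Under Registries, the surgical data requested are: "The National Patient Registry (NPR) on re-operative surgery (NCSP: KJBC00-02, KJBW96-98, KJBB00-01, KJBB96-97) and endoscopy (NCSP: KUJD02-05, KJCA55) during follow-up". Under Primary outcome, failure criterion 1 is "Having undergone reoperation (NSCP: KJBC00-02, KJBW96-98, KJBB00-01, KJBB96-97) between index date and end of follow-up", and failure is dated at the reoperation.

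The same document calls the index operation primary surgery when it defines psychiatric history, 90-day mortality, educational level and income. It never defines that term. The nearest covariate is previous abdominal surgery (yes/no), taken from the patient record and listed as a Cox candidate.

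**The concern.** The label primary surgery shows an intention to study first operations, but no rule in the plan enforces it. Entry depends on one code at one department in a fixed window, and the plan lists that code among the codes for a repeat operation. A first fundoplication outside the window or outside the hospital is not looked for.

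If such patients are present, first and repeat operations are mixed in one cohort, and the Cox model and the score built from it have no variable that identifies the repeat cases.

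A second gap concerns patients with two KJBC01 records inside the window. If the later record is taken as index, the earlier operation drops out. A patient who has already met the reoperation criterion then restarts as event-free.

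**Working it through.** The plan gives no calculation on this point. The 557 is a count of patients, not a derived sample size, so there is no figure to reproduce. The check is a comparison of codes and dates.

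**1. Is the index code on the reoperation list?** Expanding the ranges in criterion 1 gives:
- KJBC00, KJBC01, KJBC02 (3)
- KJBW96, KJBW97, KJBW98 (3)
- KJBB00, KJBB01 (2)
- KJBB96, KJBB97 (2)

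The total is 3 + 3 + 2 + 2 = 10 codes, and KJBC01 is one of them. The code alone therefore cannot tell a first operation from a redo.

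**2. Which periods does each data request cover?**

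| Item | Period requested |
|---|---|
| Anti-reflux procedure codes (National Patient Registry) | Follow-up only |
| Psychiatric diagnoses | Two years before primary surgery |
| Prescriptions | From two years before surgery to end of follow-up |

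The plan specifies a look-back where it wants history, but not for earlier anti-reflux surgery.

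**3. What happens to each type of patient under the plan as written?**

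| History | Index operation | Consequence |
|---|---|---|
| One KJBC01 in the window, none earlier | First operation | As intended |
| Earlier operation before 2002, KJBC01 in the window | Redo | Enters as primary surgery |
| Earlier operation at another hospital, KJBC01 in the window | Redo | Enters as primary surgery |
| Two KJBC01 in the window, first taken as index | First operation | Second counts under criterion 1 |
| Two KJBC01 in the window, second taken as index | Redo | First operation and its failure are lost |

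The plan does not choose between the last two rows.

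**4. Does a covariate separate the redo cases?** Previous abdominal surgery (yes/no) gives the same value to an earlier fundoplication and to any other abdominal operation, so it does not.

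**5. How many patients?** This cannot be derived from the documents. Purely as an assumption, count = share × 557:
- 1%: 0.01 × 557 = 5.6, about 6
- 2%: 0.02 × 557 = 11.1, about 11
- 5%: 0.05 × 557 = 27.9, about 28
- 10%: 0.10 × 557 = 55.7, about 56

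These counts show scale only. They do not estimate the redo share or its effect on the failure rate.

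**The case against.** The strongest reply is that the intent is clear and what is missing is a clarification. The text speaks repeatedly of primary surgery, and no redo case is shown to be in the cohort. Data are also to be extracted from each patient's record, including previous abdominal surgery, so an earlier fundoplication could be noticed there. Part of this stands: a registry look-back is not the only way to find these patients, and the statement must be that redo cases can enter, not that they do. But the record field as planned keeps only yes or no, and nothing tells the extractor to flag or exclude an earlier fundoplication.

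The Background sentence "Known causes of dissatisfaction are postoperative complication, redo-fundoplication" gives only limited support for an effect on outcome. It reads most naturally as a list of events after surgery, not as evidence that patients who enter with a redo fail more often on this composite.

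A reader might also infer several stronger things that the documents do not support:
- *That the index operation itself meets criterion 1, so all 557 patients fail on day 0.* The criterion requires a reoperation and dates failure at that reoperation; the index procedure is not one. The result arises only from a mechanical query on code and date with the index day included, and it would be noticed at once. What remains is the lack of a rule for same-day or same-admission records.
- *That every outcome is tied to primary surgery.* Among the outcomes, only 90-day mortality is.
- *That the score is stated to be for first operations only.* The Aim and the Clinical scoring system section refer to selection for surgery and to preoperative variables, without that limit.
- *That the bias can be sized from the 41.1% in the Background.* That figure is a 10-year risk of long-term PPI use from an external register study, not the failure rate of this four-part composite.

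**Conclusion.** The point holds as a gap in cohort definition. Followed as written, the plan can take a redo as the index operation, cannot identify such patients from its procedure request or its covariates, and leaves the index undefined for patients with more than one KJBC01 record.

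The size is unknown. The conclusion rests on two things: that a redo can be coded KJBC01, which the plan's own reoperation list implies, and that some patients may have had an earlier operation before 2002 or elsewhere, which the documents neither show nor exclude. If there are none, the look-back costs little and confirms the label primary surgery. This is an inexpensive improvement that removes a possible bias; it is not a flaw that invalidates the study.

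**What to change.** 1. Define the index operation as the patient's first anti-reflux procedure. This also settles the case of two KJBC01 records in the window.
2. Extend the existing National Patient Registry request for the same procedure codes to the period before the index date, and state how far back it goes. An explicit field for earlier anti-reflux surgery in the record extraction would be a useful supplement.
3. Exclude patients with an earlier record, or flag them and analyse them separately. Report their number either way.
4. Count criterion 1 only for procedures dated after the index procedure, and state how records from the same day or the same admission are treated.

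The cost is a wider date range in a request already planned, matching wording in the permissions and consent, and a few sentences in the plan. The cohort may fall slightly below 557. The change should be made before extraction: under Ethics and dissemination the personal identifier is removed after merging, so a missing look-back may be hard to add later.

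### The PPI failure criterion treats one isolated year above 60 DDD as permanent failure, the same as sustained use, and no sensitivity analysis is planned to show how much depends on it

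*Combined protocol and SAP*

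**What the plan says.** Under 'Primary outcome', the combined protocol and SAP lists four criteria, with "failure defined for each patient as at least one of the following statements being fulfilled". Criterion 2 is "Having filled prescription of >60 DDD/year of PPI in any year between index date and end of follow-up". It is dated as follows: "In case of 2), date of failure will be date of first prescription filled in the year, where >60 DDD of PPI are filled". The questionnaire criteria work differently: "In case of 3) or 4), date of failure will be end of follow-up".

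Surgery took place "from January 1, 2002 to December 31, 2013". Follow-up closes at the questionnaire: "Date of follow-up will be the date, patient filled out quality of life questionnaires as described below". No calendar date is given for that. The cohort is 557 eligible patients.

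The Background reports from a register study that "Five-, 10- and 15-year risks of long-term PPI use were 29.4%, 41.1% and 56.6"%. It does not define long-term use. It also warns that acid-suppressing drugs after surgery need not indicate abnormal acid exposure, and that the reasons for prescribing PPI to these patients are unknown.

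PPI use in DDD per year, and PPI use at follow-up with indication and prescriber, are secondary outcomes. The 'Cox regression' and 'Clinical scoring system' sections rest on the composite. No reason is given for 60 DDD or for a single year, and no alternative version of the criterion is planned.

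**The concern.** The study aims to improve patient selection by learning who benefits in the long term. Criterion 2 measures the amount filled in one year and makes it irreversible. A patient who passes 60 DDD once, then fills nothing for years and reports no symptoms at follow-up, has the same outcome as a patient on continuous treatment. With any steady background of isolated use, the share caught this way rises with each further year observed.

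At stake is what the score predicts. If isolated-year failures are a small part of the total, the criterion is a workable marker of lasting failure. If they are a large part, the score partly predicts ever having had one year of PPI use. The plan has no analysis that would tell the two situations apart.

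**Working it through.** There is no sample size, event count or derivation of the threshold to reproduce. The check asks what triggers the rule, how long patients are exposed to it, and how many it could add.

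**1. What triggers it.** The rule is strictly more than 60 DDD. That means 61 days at 1 DDD/day, or 61 / 2 = 30.5, so 31 days, at 2 DDD/day. As a share of one year, 61 / 365 = 16.7%.

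| Course | DDD | Triggers? |
|---|---|---|
| 28 days at 1 DDD/day | 28 | no |
| 56 days at 1 DDD/day | 56 | no |
| 28 days at 2 DDD/day | 56 | no |
| 90 days at 1 DDD/day | 90 | yes |
| 56 days at 2 DDD/day | 112 | yes |

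'Year' is not defined. If 90 DDD are filled as 45 on each side of a year boundary, neither year qualifies; the same 90 DDD within one year does. Calendar years and years since surgery can therefore give different failures and different failure dates.

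**2. Length of exposure.** The questionnaire date is an assumption here. Mid-2017 gives 3.5 to 15.5 years of follow-up, mid-2018 gives 4.5 to 16.5, and mid-2019 gives 5.5 to 17.5. With even accrual over the 12-year window, the share with at least 10 years is 5.5/12 = 46%, 6.5/12 = 54% and 7.5/12 = 62.5%.

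**3. Chance of at least one isolated qualifying year.** Let q be the yearly chance. It is assumed, because the documents give none, and years are taken as independent. Over n years the chance is 1 − (1 − q)^n.

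| q | 5 years | 10 years | 15 years |
|---|---|---|---|
| 0.5% | 2.5% | 4.9% | 7.2% |
| 1% | 4.9% | 9.6% | 14.0% |
| 2% | 9.6% | 18.3% | 26.1% |
| 3% | 14.1% | 26.3% | 36.7% |
| 5% | 22.6% | 40.1% | 53.7% |

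**4. Patients added at 10 years.** These percentages apply only to patients who are not already long-term users. Taking the cited 41.1% as long-term users leaves 1 − 0.411 = 0.589. Patients added = 557 × 0.589 × [1 − (1 − q)^10]. The share of PPI failures is the added proportion divided by itself plus 0.411.

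| q | Added proportion | Added of 557 | Share of PPI failures |
|---|---|---|---|
| 0.5% | 0.029 | 16 | 6.5% |
| 1% | 0.056 | 31 | 12.1% |
| 2% | 0.108 | 60 | 20.8% |
| 3% | 0.155 | 86 | 27.3% |
| 5% | 0.236 | 132 | 36.5% |

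This assumes that all 557 take part with 10 years of follow-up and that every cited long-term user exceeds 60 DDD in some year. It ignores overlap with the other failure criteria.

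**5. Effect of requiring two consecutive years.** Let a be the probability of no run of two so far with the last year not qualifying, and b the same with the last year qualifying. Start at a = 1, b = 0. Each year, a becomes (a + b)(1 − q) and b becomes (old a) × q. After 10 years the chance of a run is 1 − a − b. It is 0.02% at q = 0.5%, 0.09% at 1%, 0.35% at 2%, 0.79% at 3% and 2.1% at 5%. Multiplied by 557 × 0.589, that adds at most about 7 patients.

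**The case against.** The strongest reply is that the documents do not show a large effect. A reader might infer that many patients with lasting good results would be misclassified. That cannot be concluded: no rate of isolated years is given, and the assumed range runs from a small effect to a substantial one. Independent years may also overstate the effect, because clustering of use in the same patients would lower the number ever caught.

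Three other strong readings also fail. First, not every short course triggers the rule; the threshold already excludes courses up to 60 DDD. Second, follow-up of a decade or more cannot be assumed for the whole cohort; under the assumed dates it fits roughly half, and the last patients operated on have about 3.5 to 5.5 years. Third, the percentages in step 3 should not be set beside the cited 41.1% and 56.6%. They come close only at q = 5%, and they describe patients who are not long-term users, whereas the cited risks describe operated patients in general.

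It is also fair to say that reoperation is an ever-event too, that a Cox model of first failure is ordinary practice and allows for unequal follow-up, and that the questionnaire criteria can only be judged when the questionnaire is answered. The secondary outcomes show yearly and current PPI use. And two consecutive years is no better derived than one, and would miss intermittent relapse.

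These arguments stand against replacing the rule. They do not answer the narrower point: the Cox model allows for unequal observation time but does not change what the event means, and the secondary outcomes enter neither the model nor the score.

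**Conclusion.** The point holds in limited form. By its wording, criterion 2 makes one isolated year above 60 DDD a permanent failure, equal to sustained use, and the chance of this rises with follow-up. Nothing planned shows how far the composite, the Cox model or the score depends on it.

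The size is unknown. The range of 16 to 132 of 557 patients at 10 years is an illustration resting on assumed yearly rates of 0.5% to 5%, independent years, full participation and 10 years of follow-up for all. It shows that the effect could be minor or could matter, not which applies. The documents do not show that predictor effects are in fact distorted, nor that criterion 2 is unsuitable as the primary rule.

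Criteria 3 and 4 affect how this is judged. They list the absence of a high symptom score as failure, so read literally a patient without bothersome symptoms fails whatever the PPI use. The added effect of criterion 2 can be assessed only once that separate error is corrected.

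**What to change.** First correct the reversed wording of criteria 3 and 4. Then:

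- Keep criterion 2 as the primary rule, and state whether 'year' means a calendar year or 12 months counted from the index date.
- Pre-specify a sensitivity analysis in which criterion 2 requires more than 60 DDD in each of two consecutive years, and state how failure is dated in that version.
- Report how many failures rest only on one isolated year.
- Rerun the composite, the Cox model and the score under the sustained version, and describe predictors whose effect changes materially as dependent on the PPI definition.

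The cost is a few sentences of outcome definition and one rerun. The dated prescription fills needed are already requested through the end of follow-up. The downside is that the sustained version misses failures starting in the last year of follow-up and intermittent relapsing use; the primary rule still captures both.
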